**Appendix 4. Cockcroft-Gault Formula for Estimating GFR**

Creatinine Clearance (estimated) / Conventional mL/min =

[figure not shown]
$$((140 - \text{Age (years)}) \times \text{Weight (kg)} \times \text{Factor}^a) / (72 \times \text{Serum Creatinine (mg/dL)})$$

a Factor is equal to 0.85 in females and 1.00 in males.

### Appendix 5. Screening Procedure of Hepatitis B virus Infection

A subject will be screened for HBV infection. All patients must undergo testing for hepatitis B surface antigen (HBsAg), hepatitis B core antibody (HBcAb) and hepatitis B surface antibody (HBsAb). Refer to the following figure for the detail of screening procedure of HBV infection.

 HBV DNA assay is recommended to perform every 4 weeks.

**Appendix 6. Health Assessment Questionnaire-Disability Index (HAQ-DI)**

In this section we are interested in learning how your illness affects your ability to function in daily life. Please feel free to add any comments on the back of this page.

**Please check the response which best describes your usual abilities OVER THE PAST WEEK:**

	Without ANY Difficulty	With SOME Difficulty	With MUCH Difficulty	UNABLE To Do
DRESSING & GROOMING				
Are you able to:				
- Dress yourself, including tying shoelaces and doing buttons?	_____	_____	_____	_____
- Shampoo your hair?	_____	_____	_____	_____
ARISING				
Are you able to:				
- Stand up from a straight chair?	_____	_____	_____	_____
- Get in and out of bed?	_____	_____	_____	_____
EATING				
Are you able to:				
- Cut your meat?	_____	_____	_____	_____
- Lift a full cup or glass to your mouth?	_____	_____	_____	_____
- Open a new milk carton?	_____	_____	_____	_____
WALKING				
Are you able to:				
- Walk outdoors on flat ground?	_____	_____	_____	_____
- Climb up five steps?	_____	_____	_____	_____

**Please check any AIDS OR DEVICES that you usually use for any of these activities:**

- |                                     |                                                                                                             |
|-------------------------------------|-------------------------------------------------------------------------------------------------------------|
|  Cane       |  Devices used for dressing (button hook, zipper pull, long-handled shoe horn, etc.) |
|  Walker     |  Built up or special utensils                                                       |
|  Crutches   |  Special or built up chair                                                          |
|  Wheelchair |  Other (Specify: _____)                                                             |

**Please check any categories for which you usually need HELP FROM ANOTHER PERSON:**

- |                                                |                                 |
|------------------------------------------------|---------------------------------|
|  Dressing and Grooming |  Eating |
|------------------------------------------------|---------------------------------|

\_\_\_\_\_ Arising

\_\_\_\_\_ Walking

**Please check the response which best describes your usual abilities OVER THE PAST WEEK:**

	Without ANY Difficulty	With SOME Difficulty	With MUCH Difficulty	UNABLE To Do
HYGIENE				
Are you able to:				
- Wash and dry your body?	_____	_____	_____	_____
- Take a tub bath?	_____	_____	_____	_____
- Get on and off the toilet?	_____	_____	_____	_____
REACH				
Are you able to:				
- Reach and get down a 5 pound object (such as a bag of sugar) from just above your head?	_____	_____	_____	_____
- Bend down to pick up clothing from the floor?	_____	_____	_____	_____
GRIP				
Are you able to:				
- Open car doors?	_____	_____	_____	_____
- Open jars which have been previously opened?	_____	_____	_____	_____
- Turn faucets on and off?	_____	_____	_____	_____
ACTIVITIES				
Are you able to:				
- Run errands and shop?	_____	_____	_____	_____
- Get in and out of a car?	_____	_____	_____	_____
- Do chores such as vacuuming or yardwork?	_____	_____	_____	_____

**Please check any AIDS OR DEVICES that you usually use for any of these activities:**

- |                                                  |                                           |
|--------------------------------------------------|-------------------------------------------|
| _____ Raised toilet seat                         | _____ Bathtub bar                         |
| _____ Bathtub seat                               | _____ Long-handled appliances for reach   |
| _____ Jar opener (for jars
previously opened) | _____ Long-handled appliances in bathroom |
|                                                  | _____ Other (Specify: _____)              |

**Please check any categories for which you usually need HELP FROM ANOTHER PERSON:**

- |               |                                   |
|---------------|-----------------------------------|
| _____ Hygiene | _____ Gripping and opening things |
| _____ Reach   | _____ Errands and chores          |

**Appendix 7. Short Form -36, version 2, acute (SF-36)**

Please answer every question. Some questions may look like others, but each one is different. Please take the time to read and answer each question carefully by filling in the bubble that best represents your response.

---

## Your Health and Well-Being

---

**This survey asks for your views about your health. This information will help keep track of how you feel and how well you are able to do your usual activities. Thank you for completing this survey!**

**For each of the following questions, please mark an  in the one box that best describes your answer.**

**1. In general, would you say your health is:**

Excellent	Very good	Good	Fair	Poor
▼	▼	▼	▼	▼
 1	 2	 3	 4	 5

**2. Compared to one week ago, how would you rate your health in general now?**

Much better now than one week ago	Somewhat better now than one week ago	About the same as one week ago	Somewhat worse now than one week ago	Much worse now than one week ago
▼	▼	▼	▼	▼
 1	 2	 3	 4	 5

**3. The following questions are about activities you might do during a typical day. Does your health now limit you in these activities? If so, how much?**

	Yes, limited a lot	Yes, limited a little	No, not limited at all
a. Vigorous activities , such as running, lifting heavy objects, participating in strenuous sports .....	 1	 2	 3
b. Moderate activities , such as moving a table, pushing a vacuum cleaner, bowling, or playing golf .....	 1	 2	 3
c. Lifting or carrying groceries .....	 1	 2	 3
d. Climbing several flights of stairs .....	 1	 2	 3
e. Climbing one flight of stairs .....	 1	 2	 3
f. Bending, kneeling, or stooping .....	 1	 2	 3
g. Walking more than a mile .....	 1	 2	 3
h. Walking several hundred yards .....	 1	 2	 3
i. Walking one hundred yards .....	 1	 2	 3
j. Bathing or dressing yourself .....	 1	 2	 3

**4. During the past week, how much of the time have you had any of the following problems with your work or other regular daily activities as a result of your physical health?**

	All of the time	Most of the time	Some of the time	A little of the time	None of the time
a. Cut down on the amount of time you spent on work or other activities .....	 1	 2	 3	 4	 5
b. Accomplished less than you would like .....	 1	 2	 3	 4	 5
c. Were limited in the kind of work or other activities .....	 1	 2	 3	 4	 5
d. Had difficulty performing the work or other activities (for example, it took extra effort) .....	 1	 2	 3	 4	 5

**5. During the past week, how much of the time have you had any of the following problems with your work or other regular daily activities as a result of any emotional problems (such as feeling depressed or anxious)?**

	All of the time	Most of the time	Some of the time	A little of the time	None of the time
a. Cut down on the amount of time you spent on work or other activities .....	 1	 2	 3	 4	 5
b. Accomplished less than you would like .....	 1	 2	 3	 4	 5
c. Did work or other activities less carefully than usual .....	 1	 2	 3	 4	 5

6. During the past week, to what extent has your physical health or emotional problems interfered with your normal social activities with family, friends, neighbors, or groups?

Not at all	Slightly	Moderately	Quite a bit	Extremely
▼	▼	▼	▼	▼
 1	 2	 3	 4	 5

7. How much bodily pain have you had during the past week?

None	Very mild	Mild	Moderate	Severe	Very severe
▼	▼	▼	▼	▼	▼
 1	 2	 3	 4	 5	 6

8. During the past week, how much did pain interfere with your normal work (including both work outside the home and housework)?

Not at all	A little bit	Moderately	Quite a bit	Extremely
▼	▼	▼	▼	▼
 1	 2	 3	 4	 5

9. These questions are about how you feel and how things have been with you during the past week. For each question, please give the one answer that comes closest to the way you have been feeling. How much of the time during the past week...

	All of the time	Most of the time	Some of the time	A little of the time	None of the time
a. Did you feel full of life? .....	 1	 2	 3	 4	 5
b. Have you been very nervous? .....	 1	 2	 3	 4	 5
c. Have you felt so down in the dumps that nothing could cheer you up? .....	 1	 2	 3	 4	 5
d. Have you felt calm and peaceful? .....	 1	 2	 3	 4	 5
e. Did you have a lot of energy? .....	 1	 2	 3	 4	 5
f. Have you felt downhearted and depressed? .....	 1	 2	 3	 4	 5
g. Did you feel worn out? .....	 1	 2	 3	 4	 5
h. Have you been happy? .....	 1	 2	 3	 4	 5
i. Did you feel tired? .....	 1	 2	 3	 4	 5

10. During the past week, how much of the time has your physical health or emotional problems interfered with your social activities (like visiting with friends, relatives, etc.)?

All of the time	Most of the time	Some of the time	A little of the time	None of the time
▼	▼	▼	▼	▼
 1	 2	 3	 4	 5

11. How TRUE or FALSE is each of the following statements for you?

	Definitely true	Mostly true	Don't know	Mostly false	Definitely false
	▼	▼	▼	▼	▼
a. I seem to get sick a little easier than other people.....	 1	 2	 3	 4	 5
b. I am as healthy as anybody I know.....	 1	 2	 3	 4	 5
c. I expect my health to get worse.....	 1	 2	 3	 4	 5
d. My health is excellent.....	 1	 2	 3	 4	 5

*Thank you for completing these questions!*

**Appendix 8. FACIT-Fatigue**

**FACIT Fatigue Scale (Version 4)**

Below is a list of statements that other people with your illness have said are important. Please circle or mark one number per line to indicate your response as it applies to the past 7 days.

		Not at all	A little bit	Some- what	Quite a bit	Very much
H07	I feel fatigued .....	0	1	2	3	4
H012	I feel weak all over .....	0	1	2	3	4
An1	I feel listless ("washed out") .....	0	1	2	3	4
An2	I feel tired .....	0	1	2	3	4
An3	I have trouble starting things because I am tired .....	0	1	2	3	4
An4	I have trouble finishing things because I am tired .....	0	1	2	3	4
An5	I have energy .....	0	1	2	3	4
An7	I am able to do my usual activities .....	0	1	2	3	4
An8	I need to sleep during the day .....	0	1	2	3	4
An12	I am too tired to eat .....	0	1	2	3	4
An14	I need help doing my usual activities .....	0	1	2	3	4
An15	I am frustrated by being too tired to do the things I want to do .....	0	1	2	3	4
An16	I have to limit my social activity because I am tired .....	0	1	2	3	4

## Appendix 9. EQ-5D

By placing a checkmark in one box in each group below, please indicate which statements best describe your own health state today.

### Mobility

- I have no problems in walking about
- I have some problems in walking about
- I am confined to bed

### Self-Care

- I have no problems with self-care
- I have some problems washing or dressing myself
- I am unable to wash or dress myself

### Usual Activities (*eg, work, study, housework, family or leisure activities*)

- I have no problems with performing my usual activities
- I have some problems with performing my usual activities
- I am unable to perform my usual activities

### Pain/Discomfort

- I have no pain or discomfort
- I have moderate pain or discomfort
- I have extreme pain or discomfort

### Anxiety/Depression

- I am not anxious or depressed
- I am moderately anxious or depressed
- I am extremely anxious or depressed

## **Appendix 10. Recommended Clinical Management of Cholesterol**

Safety monitoring of a subject's lipid panel results is recommended to include an assessment of individual subject risk for cardiovascular disease. Management of lipid levels should be determined on an individual subject level due to the individualized nature of cholesterol treatment recommendations. The Third Report of the Expert Panel on Detection, Evaluation, and Treatment of High Blood Cholesterol in Adults (ATP III, National Cholesterol Education Program 2002) provides guiding principles for the intensity of lipid lowering therapy based on an individual's absolute risk for coronary heart disease (CHD). ATP III guidelines and/or Japan Atherosclerosis Society(JAS) Guidelines for Prevention of Atherosclerotic Cardiovascular Diseases 2014 should be used to determine if any lipid lowering intervention is required for a subject. Such assessments should occur throughout the study, including during the screening period and prior to randomization into the study, in light of the known co-morbidities associated with RA (e.g., metabolic syndrome, cardiovascular morbidity and mortality) and the observed increases in lipid levels in previous clinical trials with CP-690,550. Subject management of lipid elevations may be referred to the primary care physician at the discretion of the investigator.

A copy of the ATP III guidelines At-A-Glance Quick Desk Reference will be provided to each study site for reference.

### **Appendix 11. Evaluation of Potentially Malignant Tumors, Suspicious Lymphadenopathy or Possible Extra-nodal Lymphoproliferative Disorder (LPD)**

In the event of potentially malignant tumors, lymphadenopathy or possible extra-nodal lymphoproliferative disorder (LPD), which might arise in the course of this study, the following steps are to be taken.

When there is a decision to biopsy a potentially malignant tumor, lymph node, or other tissue, the investigator and/or consultants should contact the sponsor to discuss the issue and any decisions as soon as possible. It is recommended that specialists with experience in the evaluation of immunosuppressed patients be consulted.

If a biopsy for lymphadenopathy or lymphoma is to be performed, the investigator or consultant should refer to the study biopsy procedures instructions and review the following points with the surgeon and pathologist:

- Fine needle aspiration and core needle biopsy are strongly discouraged; excisional biopsy is required for accurate diagnosis;
- Tissue must be sent fresh to the pathology laboratory; the pathologist must be consulted before the procedure;
- Archive multiple frozen tissue samples, if possible;
- Include flow cytometry and cytogenetics as part of the pathologic evaluation;
- Culture for mycobacterium and fungi, if indicated;
- Collect and snap freeze peripheral blood lymphocytes for germ line evaluation (DNA);
- Archive multiple aliquots of serum samples.

For all biopsies of potentially malignant tumors, suspicious lymphadenopathy, or possible extranodal lymphoproliferative disorder (LPD), please request the pathologist to send the original slides used to make the definitive diagnosis, ancillary study reports, and the pathologist's report to the central laboratory for a blinded review by a central pathologist, to be paid for by Pfizer. Should the central pathologist make a diagnosis that is not essentially similar to the local pathologist's diagnosis, the site and the local pathologist will be notified and provided with an opportunity to consult with the central pathologist (paid for by Pfizer). Translation during this consultation, if needed, will be provided by the staff of the Pfizer Clinical Country Office or designee.

Both the local pathologist's diagnosis and the central pathologist's diagnosis will be reported in the study database.

## 1. AMENDMENTS FROM PREVIOUS VERSION(S)

NOTE: This Statistical Analysis Plan was amended after blinded data had been sent to the University of Wisconsin, which analyzed the data to report to the Data Safety Monitoring Board (DSMB). The data sets were sent on March 5 2015. None of the amended text resulted from or is otherwise based upon the review of data by DSMB.

### Amendment 2

Changes from the previous version (version 2.0, December 2, 2016) have been made for results of blinded data review.

- Corrected the method of multiple imputation for DAS28 missing values in Section 7.
- Added analysis of herpes zoster events defined by MedDRA Preferred Terms in Section 8.2.3.1 and Appendix 4.
- Added creatine kinase for descriptive, model analysis and summary of abnormalities in Section 8.2.3.2.
- Changed the use of percent change from baseline value instead of change from baseline value in triglyceride in Section 8.2.3.2.

### Amendment 1

Changes from the previous version (version 1.0, January 14, 2015) have been made for the issuance of a protocol amendment, results of blinded data review and observation of document review at Quality Gate.

- Statistical null hypothesis and alternative hypothesis were added in Section 4.1.
- Corrected definition of the difference between treatment groups in primary endpoint to in Section 4.2 and Section 8.2.1 as per protocol amendment.
- Definition of subgroups was clarified in Section 8.2.1.2.
- Analyses of safety data were clarified in Section 8.2.3.1 for adverse events, Section 8.2.3.2 for laboratory data, Section 8.2.3.3 for vital signs, Section 8.2.3.4 for electrocardiogram and Section 8.2.3.5 for physical examination.
- New Section 8.2.4 was added for analyses of other data and clarified in Section 8.2.4.1 for baseline summaries, Section 8.2.4.2 for study treatment exposure and Section 8.2.4.3 for concomitant medications and non-drug treatments.
- Added the definition of DAS28-3(CRP), DAS28-3(ESR), SDAI and CDAI as versions of the disease activity score in Appendix 2.1. Although these two endpoints are not pre-defined efficacy endpoint but will be available for further analysis if need be.

- Added Definition of Hyperlipidemia (Screen Shots) by ATP III in Appendix 3.
- Other minor revisions.

## 2. INTRODUCTION

Note: in this document any text taken directly from the protocol is *italicised*.

*Tofacitinib is a potent, selective inhibitor of the Janus Kinase (JAK) family of kinases with a high degree of selectivity against other kinases in the human genome. The immediate release (IR) formulation of tofacitinib has been approved for the treatment of rheumatoid arthritis (RA) as a twice daily (BID) regimen. Tofacitinib is being developed for the treatment of psoriasis (PsO, oral and topical), spondylarthropathies (ankylosing spondylitis [AS] and psoriatic arthritis [PsA]) and inflammatory bowel disease (Crohn's disease [CD] and ulcerative colitis [UC]).*

*The modified release (MR) formulation of tofacitinib is being studied as a disease-modifying antirheumatic drug (DMARD) for the once daily (QD) treatment of RA. The MR QD regimen has the potential to improve drug compliance of patients, patient convenience, and to offer additional dosing options for patients.*

*This study will seek to compare the efficacy and safety of the MR 11 mg QD regimen to the IR 5 mg BID regimen for the treatment of RA.*

### 2.1. Study Design

[figure not shown]
*This is a multicenter, randomized, double blind, parallel group, phase 3 study to evaluate efficacy and safety of tofacitinib MR 11 mg QD tablet compared to IR 5 mg BID tablet following 12 weeks treatment in patients with moderate to severe RA on a stable background of methotrexate (MTX).*

*Subjects will be randomized in a 1:1 ratio for the 2 treatment arms with a total sample size of approximately 200 subjects; there will be approximately 100 subjects randomized into the 11 mg MR QD group and approximately 100 patients into the 5 mg IR BID group.*

*The study design schematic for the study is represented in [Figure 1](#).*

**Figure 1. Study Design**

Approximately 100 per arm, N=200

**2.2. Study Objectives**

*Primary Objective*

1. *To demonstrate the non-inferiority for efficacy of tofacitinib MR 11 mg QD to IR 5 mg BID for the treatment of signs and symptoms in patients with active RA on a stable background of MTX, as measured by Disease Activity Score 28-4 (C-reactive protein) [DAS28-4(CRP)] change from Baseline at Week 12.*

*Secondary Objectives*

1. *To evaluate the similarity in efficacy of tofacitinib MR 11 mg QD and IR 5 mg BID for the treatment of signs and symptoms of RA, as measured by DAS28-4 erythrocyte sedimentation rate (ESR) change from Baseline, American College of Rheumatology 20% improvement (ACR20), ACR50, ACR70 responses, remission, and Low Disease Activity (LDA), at Week 12.*
2. *To evaluate the similarity in efficacy of tofacitinib MR 11 mg QD and IR 5 mg BID for physical function status as measured by health assessment questionnaire-disability index (HAQ-DI) change from Baseline at Week 12.*
3. *To evaluate the similarity in effects on patient’s health outcome measures (change from Baseline in short form 36 health survey (SF-36), functional assessment of chronic illness therapy (FACIT) fatigue and euro quality of life-5 dimensions questionnaire [EQ-5D]) of tofacitinib MR 11 mg QD and IR 5 mg BID at Week 12.*
4. *To evaluate the safety and tolerability of tofacitinib MR 11 mg QD in comparison with IR 5 mg BID in patients.*

### *Other Objective*

*The efficacy and health outcome objectives will also be evaluated at other post-Baseline visits.*

## **3. INTERIM ANALYSES, FINAL ANALYSES AND UNBLINDING**

*No interim analysis of the study data will be performed for use outside the data monitoring committee (DMC).*

Final analyses will follow the official database release.

## **4. HYPOTHESES AND DECISION RULES**

### **4.1. Statistical Hypotheses**

*The primary hypothesis associated with the statistical objective is to demonstrate non-inferiority of tofacitinib MR 11 mg QD to IR 5 mg BID as measured by DAS28-4(CRP) change from baseline at Week 12. The null hypothesis is that the treatment difference (tofacitinib MR 11 mg QD – IR 5 mg BID) is 0.6 or more, and the alternative hypothesis is that the treatment difference is less than 0.6.*

### **4.2. Statistical Decision Rules**

*If the upper bound of the 2-sided 95% confidence interval (type-I error [alpha] of 0.025 in each tail) for the difference in change from baseline in DAS28-4(CRP) between the two arms (MR 11 mg QD – IR 5 mg BID) is less than 0.6, then the treatment of tofacitinib MR 11 mg QD will be declared to be non-inferior to that of tofacitinib IR 5 mg BID.*

## **5. ANALYSIS SETS**

### **5.1. Full Analysis Set**

*The full analysis set (FAS) will include all subjects who were randomized and received at least one dose of the randomized investigational drug.*

### **5.2. ‘Per Protocol’ Analysis Set**

*The Per Protocol Analysis Set (PPAS) will be a subset of the FAS dataset. The PPAS will include all randomized subjects who completed the 12 week study with no important protocol deviations that could impact the efficacy analysis. The list of potentially important protocol deviations (pIPDs) and the subjects to be excluded from the ‘Per Protocol’ analysis set will be identified, reviewed, and finalized prior to the release of the database.*

### **5.3. Safety Analysis Set**

The Safety Analysis Set will include *all subjects who were randomized and received at least one dose of the randomized investigational drug. By definition, it is identical to the full analysis set defined above.*

### **5.4. Other Analysis Sets**

None.

### **5.5. Treatment Misallocations**

If a patient was:

- Randomized but not treated, then the patient will be excluded from all analyses according to the definitions of FAS, PPAS and Safety Analysis Set given above. The patient will be included in the disposition summaries.
- Treated but not randomized, then the patient will be excluded from all analyses according to the definitions of FAS, PPAS and Safety Analysis Set given above. The patient will be included in safety data listings.
- Randomized but took incorrect treatment, then the patient will be reported under his/her randomized treatment group for all analyses based on FAS and Safety Analysis Set, but will be omitted from analyses based on PPAS. Medication errors will be listed.

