#### **5.4.1. Dosage Form(s) and Packaging**

Subjects will be randomized to receive either tofacitinib MR 11 mg QD or tofacitinib IR 5 mg BID. The following medication will be provided by the sponsor and dispensed for oral administration:

- Tofacitinib MR 11 mg tablets
- Placebo tablets to match tofacitinib MR 11 mg tablets
- Tofacitinib IR 5 mg tablets
- Placebo tablets to match tofacitinib IR 5 mg tablets

The IR 5 mg and the matching placebo tablets are identical in appearance. The MR 11 mg and the matching placebo tablets are identical in appearance.

Study medication will be packaged in two bottles. Each bottle will be labeled appropriately. Refer to investigational product manual for details on clinical packaging.

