### **8.2.3. Analysis of Safety Data**

*The safety analysis will be conducted on the safety analysis set.*

The Sponsor has standard (i.e., used for all its clinical trials) summary displays and listings for MedDRA-coded adverse events, demography, medical history, length of time in study and discontinuation, concomitant and concurrent medications, physical examination, ECG, laboratory tests, weight, pulse rate, and blood pressure. These standards, called Pfizer Data Standards, will be utilized in the reporting of these routine safety variables (Pfizer Data Standards Rulebook).

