### 8.2.3.1. Adverse Events

Adverse events will be listed and summarized within treatment group in accordance with the Pfizer Data Standards. Adverse events, serious adverse events and discontinuation due to adverse event will also be summarized by subsets described in Section [8.2.1.2](#).

Adverse events met following the Standardised MedDRA Queries (SMQs) will be summarized within treatment group.

- Hypertension
- Congestive Heart Failure
- Dyslipidaemia
- Erythropenia
- Leukopenia
- Acute Renal Failure
- Ischemic Heart Disease
- Ischemic Cerebrovascular Disease
- Myocardial Infarction
- Possible Drug-Related Hepatic Disorders

Serious infection events and treated infection events will be summarized per visit, respectively.

Herpes zoster events defined by MedDRA Preferred Terms in [Appendix 4](#) will be summarized within treatment group.

Adverse events reviewed in the following adjudication/review committees will be listed.

- Cardiovascular safety endpoints adjudicated by the Cardiovascular Endpoint Adjudication Committee (CV-EAC).
- Malignancies adjudicated by Malignancy Adjudication Committee (MAC)
- Opportunistic infections reviewed by the Opportunistic Infection Review Committee (OIRC).
- Hepatic events reviewed by the Hepatic Event Review Committee (HERC).

- Gastrointestinal perforation events reviewed by Gastrointestinal Perforation Review Committee (GIPRC).
- Interstitial lung disease (ILD) events reviewed by the Interstitial Lung Disease Review Committee (ILDRC).
- Potentially malignant tumors, suspicious lymphadenopathy, possible extranodal lymphoproliferative disorder (LPD) reviewed by the central pathologists.

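### SAP 5.5 keeps a subject who took only the other arm's regimen under the randomized arm in the safety tables; grouping safety by treatment received is a minor, cheap improvement

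*SAP*

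**What the plan says.** SAP 5.5 has a bullet for the subject who was randomized but took incorrect treatment. That subject "will be reported under his/her randomized treatment group for all analyses based on FAS and Safety Analysis Set", is left out of the per-protocol set, and appears in a listing of medication errors.

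The rule carries through to the safety output:

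- Under the heading "5.4. Other Analysis Sets" the SAP enters none.
- SAP 8.2.3: "The safety analysis will be conducted on the safety analysis set".
- SAP 8.2.3.1: "Adverse events will be listed and summarized within treatment group in accordance with the Pfizer Data Standards". It does not say whether the group is the assigned or the received one, so the rule in 5.5 is the only one stated. Selected laboratory tests and blood pressure are also modelled by treatment (SAP 8.2.3.2 and 8.2.3.3).
- Protocol 9.3 gives no grouping by treatment received.

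On membership, SAP 5.1 reads "The full analysis set (FAS) will include all subjects who were randomized and received at least one dose of the randomized investigational drug". SAP 5.3 asks that the subject "received at least one dose of the randomized investigational drug. By definition, it is identical to the full analysis set defined above". Protocol 9.3 defines the safety set without the word randomized before the drug, yet also calls it identical to the full analysis set.

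**The concern.** Grouping by assigned arm is right for the FAS, because it preserves the randomized comparison. A safety table answers a different question: what happened to people exposed to each formulation. The safety and tolerability of MR compared with IR is a secondary objective (SAP 2.2), and the summary tables are where it is read. If a subject took only the other arm's regimen, the plan counts that subject's events, and that subject in the denominator, under the formulation not taken. No planned safety summary corrects this, since the per-protocol set serves only the efficacy robustness analysis (SAP 8.2.1.1). The SAP foresees the situation: incorrect treatment is a named deviation class in SAP 5.6.2.

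**Working it through.** The plan states no figure for this point. The only planned number used is 100 subjects per arm (Protocol 9.1). The sample size calculation behind it reproduces: 2 × (1.960 + 1.282)² × 1.3² / 0.6² = 98.7, so 99 per arm or 198 in all, against the stated 200. Nothing below changes it.

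**Step 1. Which errors does the rule misattribute?** Protocol 5.4.1: "Study medication will be packaged in two bottles". Under Protocol 5.5 every subject takes tablets from both bottles, so the contents matter as a pair.

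| Assigned | MR bottle | IR bottle | Drug received |
|---|---|---|---|
| MR | active | placebo | MR, as assigned |
| MR | placebo | active | IR: full switch |
| MR | active | active | both |
| MR | placebo | placebo | neither |
| IR | placebo | active | IR, as assigned |
| IR | active | placebo | MR: full switch |
| IR | active | active | both |
| IR | placebo | placebo | neither |

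Only a full switch puts the subject wholly on the other arm's regimen. Drug is dispensed at three visits (Protocol 5.4), so the switch must also hold throughout for the whole exposure to belong to the other arm. Subjects on both actives, on neither, or on a mixture over time have no clean arm to move to.

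**Step 2. Rare event.** Assumptions, not from the documents: one IR-assigned subject took the full MR regimen throughout and had the event; one correctly treated MR subject also had it; nobody else did.

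- As randomized (SAP 5.5): MR 1/100 = 1.0%, IR 1/100 = 1.0%.
- By treatment received: MR (1 + 1)/(100 + 1) = 2/101 = 2.0%, IR (1 − 1)/(100 − 1) = 0/99 = 0.0%.

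**Step 3. Common event.** Assumptions: 10 subjects with the event in each arm as randomized, and one IR-assigned subject fully switched to MR.

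- As randomized: 10/100 = 10.0% in each arm.
- By treatment received, if the switched subject had the event: MR 11/101 = 10.9%, IR 9/99 = 9.1%.
- By treatment received, if not: MR 10/101 = 9.9%, IR 10/99 = 10.1%.

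**Step 4. No switch.** The two groupings coincide and the effect is zero.

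**The case against.** The strongest reply is that this is an explicit, pre-specified choice, consistent with a safety set declared identical to the FAS, and that nothing in the documents forbids it. That is fair: the rule is a convention that could be improved, not a contradiction in the plan.

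Other parts of the reply also stand:

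- **The class is likely to be small or empty.** Treatment is assigned by IWRS/IVRS code (Protocol 5.1) and dispensed by unique container number (Protocol 5.4.2). A full switch needs both bottles wrong throughout.
- **Events are not lost.** All adverse events are listed as well as summarised. Medication errors have their own CRF page whether or not an event occurs (Protocol 8.4). SAP 8.2.3.1 adds: "Adverse events reviewed in the following adjudication/review committees will be listed". A reader could match a switched subject to that subject's events, although a listing does not correct the table.
- **The sponsor's data standards are not in the documents.** They might hold an actual-treatment convention. If so, it would conflict with the sentence in SAP 5.5, which would still need changing.

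A reader might infer that a single wrong bottle also biases the comparison in a way regrouping would cure. It would not: that subject received both actives or neither, belongs to neither column, and stays under the randomized arm with or without the change.

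A reader might also infer that SAP 5.1 and 5.3 drop a subject who never took the assigned drug from every table. Taken alone, their wording allows that. But SAP 5.5 reports such subjects in both sets and is naturally the governing rule, so this is a wording mismatch and not a planned exclusion.

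**Conclusion.** The point holds as a minor one. As written, SAP 5.5 would tabulate the events of a fully switched subject under the formulation not taken, in tables that serve a stated secondary objective, and no summary by treatment received is stated.

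The size depends on an occurrence for which the documents give no rate. Without a full switch the effect is zero. With one, a common event moves each arm's percentage by less than one point in the illustration, and only a rare-event count could look visibly different. The counts shown rest on assumed events and one assumed switch; they are not a forecast.

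A reader might infer that the MR versus IR safety comparison is materially biased. The documents do not support that. The plan states no adverse-event risk difference or interval as an output and no safety hypothesis, so there is no formal inference to distort. The primary non-inferiority analysis, its error rate and the sample size are untouched.

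**What to change.** Before unblinding:

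1. **SAP 5.5.** Limit reporting under the randomized group to the FAS. State that the Safety Analysis Set is summarised by treatment actually received.
2. **SAP 5.5, regrouping rule.** A subject is regrouped only if the whole exposure was the other arm's two-bottle regimen. Subjects who received both actives, neither active, or a mixture of regimens stay under the randomized arm and are flagged and listed separately with their events.
3. **SAP 5.3.** Drop the word randomized before the drug, matching Protocol 9.3, so that a subject who took only the wrong regimen is plainly in the safety set. Membership can stay the same as the FAS under SAP 5.5; say that only the grouping differs.

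Protocol 9 lets the SAP modify the analysis plan. It requires a protocol amendment only for major changes to the primary endpoint or its analysis, so none is needed for this. No new data collection is required. The costs are one more SAP revision, one actual-treatment variable, and slightly different denominators between efficacy and safety tables if a switch occurs, such as 101 and 99 instead of 100 and 100.
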